- 3.3.3** Known cerebral/meningeal disease.
- 3.3.4** Any active systemic viral, bacterial, or fungal infection requiring IV treatment with antimicrobial therapy within 1 week prior to first dose.
- 3.3.5** Patients with known HBsAg positive HBV infection. Patients with prior history of Hepatitis B infection, but immune, with only IgG Hepatitis core antibody + (HBcAb +) must receive anti-viral prophylaxis (e.g., lamivudine 100mg po daily) for at least 1 week prior to cycle 1 and throughout induction and continuation therapy and for at least 6 months after the last SGN-35 dose. In addition, consultation with a hepatologist is recommended.
- 3.3.6** Patients with a known hypersensitivity to any excipient contained in the drug formulation.
- 3.3.7** Patients with dementia or an altered mental state that would preclude the understanding and rendering of informed consent.
- 3.3.8** Patients with a prior history of documented pancreatitis.
- 3.3.9** Patients with severe renal impairment (CrCL <30 mL/min). A calculated CrCl is acceptable.

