Patients 23 through 45 are not required to have a restaging PET or CT scan after the first 2 ‘lead in’ cycles of SGN35. PET and/or CT scans may be obtained at the investigators discretion at this time point. If there is documented progressive disease after SGN35 (i.e., prior to initiation of AVD), patients may still remain ‘on trial’ and proceed to AVD chemotherapy, however they will not receive SGN35 consolidation.

5.2.8.2 Re-staging for chemotherapy intolerant patients.

See Section 5.3.3.8 for this definition. Chemotherapy intolerant patients may proceed with consolidation SGN35 therapy if they have achieved either a PR or CR at time of chemotherapy intolerant designation. These patients should have repeat staging CT scans performed prior to initiation of SGN35 consolidation therapy (if not done within the preceding 30 days).

5.3 AVD chemotherapy.

5.3.1 Dosing.

Chemotherapy	Dose	Infusion	Timing
Doxorubicin (adriamycin)	25 mg/m ²	IV	Days 1 and 15
Vinblastine (velban)	6 mg/m ²	IV	Days 1 and 15
Dacarbazine	375 mg/m ²	IV	Days 1 and 15

(DTIC)			
--------	--	--	--

NOTE: A cycle is 28 days. Use actual weight to calculate body surface area. For further information regarding drug administration, please see Section 8.2.

5.3.2 Number of cycles.

Patients will receive 6 cycles of AVD chemotherapy, unless judged by the treating physician to be chemotherapy intolerant (see section 5.3.3.8). Each cycle is scheduled to be repeated every 28 days.

5.3.3 Dose modifications.

NOTE: All toxicities should be graded according to the CTC (version 4.0).

5.3.3.1 Hematologic Toxicity.

Dose delays and reductions of AVD chemotherapy only are to be done at the discretion of the treating physician and must be clearly documented on the Treatment eCRF in NOTIS along with the CTC (version 4.0) grade. Delays of greater than 3 weeks due to AVD toxicity must be approved by the PI and the QAM must be included on this correspondence. The following are only recommendations (are not mandatory) for modifications for AVD; SGN modifications are mandatory and are described above in Table 3. Some guidelines to be considered are for absolute neutrophil count of <500 on the day of treatment would be to consider addition of G-CSF (filgrastim) therapy. This is strongly preferred due to the long half-life of pegfilgrastim.

Patients with persistent severe neutropenia, especially despite use of granulocyte growth factor, could have reduction of doxorubicin and vinblastine by 25%.

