5.3.4.2 Growth factor

Granulocyte colony stimulating factor (e.g., G-CSF) may be used at the discretion of the treating physician as above and in accordance with ASCO guidelines; however as noted in Section 5.3.3.1, G-CSF would be advocated (filgrastim) vs pegfilgrastim. Please record all granulocyte (or erythrocyte) colony stimulating factors on the treatment forms.

5.3.5 Re-staging.

All patients will have re-staging FDG-PET and re-staging CTs of the neck/chest/abdomen/pelvis performed after the 3rd cycle of AVD.

Recommended timing of these scans are between days 22 and 25 of the 3rd cycle. All patients will also have re-staging CTs of the neck/chest/abdomen/pelvis performed at the completion of AVD (i.e., after the 6th cycle).

FDG-PET will only be repeated at this time (end of AVD) if the patient has not entered into complete remission (CR). See **Section 6.0** for further details regarding assignment of response and see Table 3 Schedule of Activities in Section 7.0 for additional details. Any patient who has not achieved a CR or PR after the 6 cycles of AVD should be taken off study at this point and not proceed with SGN-35 consolidation therapy.

5.4 SGN-35 consolidation.

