5.4.2 Dosing

Dosing of SGN-35 in this consolidation phase will start at **1.8 mg/kg or 1.2 mg/kg (depending in part on presence of neurotoxicity during SGN-35 lead-in and AVD chemotherapy)**.

5.4.2.1 The intent is to start all SGN-35 consolidation 2 weeks after the last dose/administration of AVD therapy. Furthermore, irrespective of dose, SGN-35 consolidation therapy will be given once every 3 weeks for 4 doses.

5.4.2.2 Patients who had **no neurotoxicity-related dose reductions** during the lead-in SGN-35 or vinblastine therapy may start SGN-35 consolidation at **1.8 mg/kg**.

5.4.2.3 Patients who had **any neurotoxicity-related dose reduction(s)** (or discontinuation) of the lead-in SGN-35 and/or vinblastine therapy will start SGN-35 consolidation at **1.2 mg/kg**.

5.4.2.4 If patients have **“ongoing”** grade 2, 3, or 4 neurotoxicity at the time of initiation of SGN-35 consolidation, therapy **must be delayed** until recovery to grade 1 (delay up to 8 weeks after completion of last AVD dose are permitted). If neurotoxicity does not recover to grade 1 within 8 weeks, then SGN-35 consolidation will not be given.

5.4.2.5 *Additionally*, if there are **other toxicities** whereby the treating physician believes it would be **best medical practice** to delay SGN-35 consolidation (up to 6 weeks) and/or initiate at the lower 1.2 mg/kg dose level, such decisions may be evaluated on a case-by-case basis, but should be discussed with the study PIs; the QAM should also be included on all such correspondence.

5.4.3 Dose modifications.

Intra-patient dose reduction to 1.2 mg/kg or to 0.8 mg/kg will be allowed depending on the type and severity of toxicity. Table 2 describes the recommended dose modifications for study treatment-associated toxicity. Additionally, the start of a subsequent SGN35 cycle may be delayed for up to 4 additional weeks if additional time is required for the patient to recover from study treatment-associated toxicity experienced during the current cycle.

NOTE: *SGN-35 doses reduced for treatment-related toxicity should not be re-escalated.*

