Serum Chemistries (electrolytes, SGOT, SGPT, total bilirubin, direct bilirubin, ⁵ LDH, creatinine, glucose, alkaline phos, and calcium)	X	X	X	X	X ¹³
Serum amylase and lipase ¹⁷	X	X		X	
ESR	X	X	X	X	
Uric acid ¹⁶	X				
Bone marrow biopsy (bilateral preferred, unilateral acceptable) ⁶	X				
EBV PCR ¹⁶	X		Day 1, cycle 1	On start of cycle 1	At end of and 6 months after consolidation
TSH and Hemoglobin A1c ¹⁶	X			On start of cycle 1	
HIV screening ⁷	X				
Echo or MUGA	X		X ⁸		
CT Chest, Abdomen, and Pelvis ^{9, 10, 15}	X	X	X ¹⁵	X ¹⁰	X ¹³
PET/CT Scan ^{9, 10}	X	X	X		
Co-morbidity/ADL assessment ¹¹	X				X ¹¹
Quality of life assessments ¹²	X		X	X	X
SGN-35 PK sample ¹⁸		X			

Correlative science blood studies ¹⁴				
	X	X	X	X
1. Two cycles of therapy given 21 days apart (+/- 7 days). Patients may be evaluated in the office more frequently, if needed, at physician discretion. If there is documented progressive disease after SGN35 (i.e., prior to initiation of AVD), patients may still remain 'on trial' and proceed to AVD chemotherapy, however they will not receive SGN35 consolidation. Study visits, tests, and procedures should be completed Day 1 (+/- 2 days) of each cycle.				
2. Six cycles of therapy. Cycles are every 28 days (+/- 7 days), though treatments are given day 1 and day 15 of each cycle. Patients may be evaluated in the office more frequently, if needed, at physician discretion. Study visits, tests, and procedures should be completed Day 1 (+/- 2 days) of each cycle.				
3. Four cycles of therapy. Cycles are every 21 days (+/- 7 days). Patients may be evaluated in the office more frequently, if needed, at physician discretion. Study visits, tests, and procedures should be completed Day 1 (+/- 2 days) of each cycle.				
4. CBC at baseline and as clinically indicated to capture nadir: please record the absolute lymphocyte count.				
5. Direct bilirubin is recommended, but required only if total bilirubin is elevated.				
6. Baseline bone marrow biopsy is mandatory within 90 days prior to starting treatment. Repeat bone marrow biopsy at time of CR and relapse ONLY if positive at baseline (bilateral biopsy is preferred, but unilateral is acceptable). .				
7. Not mandatory, but recommended.				
8. Repeat after 4 th cycle of AVD. May be repeated earlier or more frequently as clinically indicated.				

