Vials containing study treatment must be refrigerated at 2–8°C in a secure location (e.g., locked room) accessible only to the pharmacist, the investigator, or a duly designated person. Study treatment does not contain preservatives; therefore, opened and reconstituted vials of study treatment must be used on the same day when stored under refrigeration at 2–8°C. Reconstituted SGN-35 should not be stored at room temperature. It is recommended that study treatment vials and solutions be protected from direct sunlight until the time of use. Reconstituted vials must not be shaken.

8.1.5 **Dose specifics.** Dosing is based on patient weight according to the institutional standard; however, doses will be adjusted for patients who experience a $\geq 10\%$ change in weight from baseline. Actual weight will be used except for patients weighing greater than 100 kg; dose will be calculated based on 100 kg for these individuals. The dose will be rounded to the nearest whole number of milligrams.

8.1.5.1 Dosing for the first 2 cycles of the SGN-35 lead-in are administered at 1.8 mg/kg given 3 weeks apart.

8.1.5.2 Dosing for the 4 cycles of consolidation (i.e., after induction AVD chemotherapy), SGN-35 dosing is 1.8 mg/kg or 1.2 mg/kg given every 3 weeks apart for 4 doses. See **Section 5.4.2** for details.

8.1.5.3 For SGN-35 dose modifications, see **Sections 5.2.5 and 5.4.3** as well as Table 2.

8.1.6 **Preparation.** Procedures for proper handling and disposal of anticancer drugs should be considered. Several guidelines on this subject have been published (see manufacturer's prescribing information insert). Use appropriate aseptic technique for reconstitution and preparation of dosing solutions.

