10.5 Termination of Treatment and/or Study Participation

Patients will be informed that they have the right to withdraw from the study at any time for any reason, without prejudice to their medical care. The investigator also has the right to withdraw patients study treatment for any of the following reasons:

- Intercurrent illness
- Occurrence of an unacceptable adverse event
- Patient request (follow-up may still be permitted unless patient withdraws consent from the study as a whole)
- Protocol violations
- Non-compliance
- Administrative reasons
- Failure to return for follow-up
- General or specific changes in the patient's condition unacceptable for further treatment in the judgment of the investigator
- Progressive disease at any time

If treatment is ongoing at the time of termination, patients should return 30 days after the last study treatment for a “termination visit” that includes the assessments specified for the 30-day follow-up visit. If this is not possible or if the patient has completed study treatment more than 30 days before, these assessments should be done at the time of termination.

If a patient has terminated the study as a whole (withdraws consent), no further data collection and submission is permitted, except for follow-up of AE’s present at the time of termination. If, however, a patient is withdrawn from treatment (but not the study as a whole), follow-up for survival endpoints will continue.

Patients may choose to stop study treatment and/or withdrawn from the study as a whole for any reason without jeopardizing their relationship with their health care providers.

- 10.5.1 **Accountability for Study Drug.** Seattle Genetics Clinical Affairs (the Supporter) or its designee will ship vials of SGN-35 directly to each study center.

The individual receiving the shipment must verify the quantities received. The Clinical Supplies Shipping Receipt contained in the shipment must be signed, dated, and returned to the Supporter or its designee. An overall summary of all clinical supplies received, used, and returned per patient must be maintained by each study center. Seattle Genetics will provide full accountability for shipments of drug to individual sites. Seattle Genetics will NOT assume accountability of drug within the individual sites.

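### Section 3.3.5 times hepatitis B prophylaxis from the last SGN-35 dose only, so a patient who completes six on-schedule AVD cycles, gets no consolidation and is not awaiting it has a required minimum of about 1–2 weeks after chemotherapy

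*Combined protocol and SAP*

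**What the plan says.** Section 3.3.5 sits among the exclusion criteria. It admits patients with past hepatitis B who are immune and positive for core antibody only, provided they take an antiviral. The drug starts at least a week before cycle 1 and continues "throughout induction and continuation therapy and for at least 6 months after the last SGN-35 dose". The same criterion recommends consulting a hepatologist. No other section sets a prophylaxis period after AVD.

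AVD itself is covered, because section 8.1.5.2 places consolidation "i.e., after induction AVD chemotherapy". Continuation therapy is not one of the three phases named in section 5.1; I read it as SGN-35 consolidation.

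Four routes lead to AVD without consolidation:

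- Progression after lead-in (5.2.8.1, repeated in Table 4 footnote 1): patients may go on to AVD, "however they will not receive SGN35 consolidation".
- Less than PR after six AVD cycles (5.3.5): the patient "should be taken off study at this point and not proceed with SGN-35 consolidation therapy".
- Persistent neurotoxicity (5.4.2.4): "If neurotoxicity does not recover to grade 1 within 8 weeks, then SGN-35 consolidation will not be given".
- Stopping during or after AVD (10.5): "The investigator also has the right to withdraw patients study treatment for any of the following reasons", with a list that includes adverse events, intercurrent illness and patient request.

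**The concern.** The 6-month clock is tied to one drug, while the regimen has two components and SGN-35 is not always the last one given. On any of the four routes the last SGN-35 dose is the second lead-in dose, so the clock runs while the patient is receiving AVD. By the end of a full AVD course it has almost expired.

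Two patients with the same six AVD cycles therefore have very different mandatory cover after treatment, depending only on whether consolidation was given. No section gives a reason for this. Other post-treatment clocks in the protocol run from the end of treatment in general: the follow-up visit in 7.1.3 and the expedited-reporting period in 10.3.2. What is at stake is a mandatory safety rule that nearly lapses for a small subgroup. The trial's efficacy inference is not affected.

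**Working it through.** **Inputs.** Lead-in: two SGN-35 doses 21 days apart (5.2.2). AVD: six 28-day cycles, dosed on days 1 and 15 (5.3.1, 5.3.2). Consolidation: "The intent is to start all SGN-35 consolidation 2 weeks after the last dose/administration of AVD therapy" (5.4.2.1), then four doses every 3 weeks. Six calendar months are 181–184 days, depending on the start date. Day 1 is the first SGN-35 dose.

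**Schedule.**

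- Lead-in dose 2: 1 + 21 = day 22.
- AVD cycle 1 day 1: 22 + 21 = day 43.
- Last AVD dose after c cycles: 43 + 28(c − 1) + 14. For c = 6 this is day 197.
- End of cycle 6: 43 + 6 × 28 − 1 = day 210.

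**The rule as it works for a consolidated patient.** Consolidation starts on day 197 + 14 = 211, and dose 4 falls on day 211 + 63 = 274. The clause ends on day 274 + 181 to 274 + 184 = 455–458, which is 181–184 days after all therapy.

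**Six on-schedule cycles, no consolidation and none pending.** The 6-month clock ends on day 22 + 181 to 22 + 184 = 203–206.

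- Narrow reading, with induction ending at the last infusion: 203 − 197 to 206 − 197 = 6–9 days.
- Wider reading, with induction running to the end of cycle 6: the clock has already expired, and the induction clause sets the floor at 210 − 197 = 13 days.

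**Timing shifts.** Table 4 footnote 2 permits a window: "Cycles are every 28 days (+/- 7 days), though treatments are given day 1 and day 15 of each cycle". On the narrow reading:

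- A total delay of 7 days puts the last dose on day 204 and leaves −1 to 2 days, that is 0–2.
- A delay of 14 days (day 211) leaves −8 to −5, that is none.
- A shift 7 days earlier (day 190) leaves 13–16 days.

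On the wider reading, a delay moves the end of cycle 6 along with the last dose, so the floor stays near two weeks.

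**AVD stopped early, no consolidation.**

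| Cycles given | Last AVD dose | Cover remaining to day 203–206 |
|---|---|---|
| 3 | day 113 | 90–93 days |
| 4 | day 141 | 62–65 days |
| 5 | day 169 | 34–37 days |
| 6 | day 197 | 6–9 days (narrow reading) |

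**Waiting for neurotoxicity to recover.** The wait may last until day 197 + 56 = 253. A site that still plans consolidation would be expected to continue the antiviral, which gives up to 56 days after AVD. If consolidation is then ruled out, the 6 months have passed and nothing further is required.

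**Number of patients (both rates are assumptions).** If 10–30% of 48 patients receive AVD without consolidation, that is 4.8–14.4, or about 5–14. If 2–10% of these are core antibody positive, the expected number is 5 × 0.02 = 0.1 to 14 × 0.10 = 1.4. This counts all unconsolidated patients, including early stoppers, so the six-cycle group is smaller. Table 4 lists no hepatitis B serology, so only patients already known to be positive would be reached.

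**The case against.** The strongest reply is that the gap is narrow and has safeguards around it. Six months is a floor, and a hepatologist, if consulted, can set a longer course. Liver chemistry is part of the blood tests every 3 months in follow-up, which Table 4 footnote 13 extends to patients who stop early for adverse events or progression. All of this stands and limits the severity. But the consultation is only recommended, and liver tests can detect a problem without replacing the prophylaxis that the section makes mandatory.

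A reader might infer that every unconsolidated patient is left with about a week, or with nothing after a short delay. The documents do not support that. The zero arises only if induction ends at the last infusion. With a 28-day cycle, induction can equally be read to end with cycle 6, and the floor then moves with any delay. Patients who stop AVD early, or who are still awaiting consolidation, have longer cover.

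A reader might also infer that the clause exposes patients to a known risk of reactivation. No section gives that risk, or the duration needed after AVD alone. Applying the same 6 months is a judgment that extends the protocol's own standard.

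It is also fair that a longer clause has limited force for patients who are taken off study or withdraw.

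**Conclusion.** The inconsistency is real and minor. The mandatory minimum after the last AVD dose is about 1–2 weeks for a core-antibody-positive patient with six on-schedule cycles and no consolidation given or pending, against 181–184 days after all therapy for a consolidated patient.

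The size rests on three things: the nominal schedule, AVD starting 21 days after lead-in dose 2, and where induction is taken to end. The gap in the text does not depend on these. Section 3.3.5 has no clock for the last AVD dose, and no other section supplies one. The number of patients rests on assumed rates and may well be zero in a trial of 48.

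**What to change.** In section 3.3.5, replace 'the last SGN-35 dose' with 'the last dose of any protocol treatment (SGN-35 or AVD)'. For an unconsolidated patient with six on-schedule cycles, the minimum then ends on day 197 + 181 to 197 + 184 = 378–381. Nothing changes for consolidated patients.

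The cost is a one-phrase amendment with no new visits or tests. The affected patients take the oral antiviral for longer. The 6-month clock ends 197 − 22 = 175 days later after six cycles, and 147, 119 or 91 days later if AVD stops after cycle 5, 4 or 3. Anyone who would have continued the drug anyway, for example during a neurotoxicity wait, takes on less extra treatment than this. For patients who leave the study, the new wording would serve mainly as guidance to the treating physician.
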